#### 1. BACKGROUND AND RATIONALE

#### 1.1 BACKGROUND

GARDASILTM is Merck's quadrivalent human papillomavirus (HPV) vaccine. The vaccine was approved in 2006 by the United States (US) Food and Drug Administration (FDA) and European Medicines Agency (EMEA) for the prevention of several diseases caused by HPV types 6, 11, 16, and 18 in females. In October 2009, the US FDA approved GARDASILTM for use in boys and men, 9 through 26 years of age, for the prevention of external genital warts (condyloma acuminata) caused by HPV types 6 and 11. In December 2010, the US FDA approved GARDASILTM for use in males and females, 9 through 26 years of age, for the prevention of anal intraepithelial neoplasia (AIN) grades 1, 2, and 3 caused by HPV types 6, 11, 16, and 18, and for the prevention of anal cancer caused by HPV types 16 and 18.

GARDASILTM is an aluminum adjuvanted recombinant protein particulate (virus-like particle [VLP]) vaccine that contains 20 µg HPV 6 L1 VLP, 40 µg HPV 11 L1 VLP, 40 µg HPV 16 L1 VLP, and 20 µg HPV 18 L1 VLP, along with 225 µg of amorphous aluminum hydroxyphosphate sulfate [1]. GARDASILTM is administered intramuscularly as a 0.5-mL dose according to the following schedule: 0, 2 and 6 months.

Human papillomavirus (HPV) is a family of small DNA viruses and is the most commonly detected sexually transmitted virus in men and women [2]. In men, HPV anogenital infection can result in anogenital diseases, including condyloma acuminata or anogenital warts, intraepithelial neoplasia, and carcinoma of the penis and anus [2]. These diseases are associated with substantial morbidity and mortality [3]. In females, persistent genital HPV infection can cause cervical cancer, other types of anogenital cancers and genital warts [2].

This study intends to build on the large body of safety experience from the administration of GARDASILTM to females, including a large post-licensure observational safety study. In clinical trials involving the administration of GARDASILTM to young males, the vaccine was generally well tolerated. No serious adverse events have been identified to be associated with GARDASILTM in the randomized clinical trials involving over 3,000 young male recipients of GARDASILTM.

#### 1.2 STUDY RATIONALE

This observational study is being conducted as a post-licensure regulatory commitment after the October 2009 approval of GARDASILTM in males. This study will include males vaccinated with GARDASILTM in a large US health plan. The objective of the study is to assess the safety of GARDASILTM in the general population of males for whom the vaccine is approved.

Protocol/Amendment No.: 070-01

#### 1.3 STUDY SETTING

The study will be conducted in collaboration with PPD The study population will be drawn from a proprietary research database containing eligibility, pharmacy claims, and medical claims data from a large US health plan affiliated with This study in males includes features that are methodologically similar to those used for the safety study of GARDASILTM in females.

All of the statistical analyses will be performed by PPD Study results will be provided for review and interpretation to the Safety Review Committee (SRC), an independent committee of experts, external to PPD and the SPONSOR, in charge of monitoring the safety data emerging from the study.

#### 2. OBJECTIVES AND HYPOTHESES

#### 2.1 PRIMARY OBJECTIVE

The primary objective of this study is to describe the general safety of GARDASILTM among males within 60 days following the administration of *each dose* of the vaccine by estimating: a) the incidence of health outcomes resulting in emergency room visits or hospitalizations occurring in combined 60-day risk periods after each dose of GARDASILTM; and b) the relative risk of such health outcomes as compared to incidence rates in a post-vaccination self-comparison reference period.

#### 2.2 SECONDARY OBJECTIVES

The three secondary objectives of this study are:

- 1. To describe the general safety of a first dose of GARDASILTM in males by estimating: a) the incidence of health outcomes resulting in emergency room visits or hospitalizations in the 60-day risk period following the first dose of GARDASILTM; and b) the relative risk of such health outcomes as compared to incidence rates in a post-vaccination self-comparison reference period.
- 2. To provide descriptive epidemiology of the following pre-specified new-onset conditions for a period of 6 months after each dose of GARDASILTM, including comparison of incidence of these new-onset conditions, identified from the outpatient, emergency room, and hospital setting, to background incidence within the PPD male population of similar age distribution. These pre-specified conditions are considered conditions of interest, although no safety signals have been found in the GARDASILTM trials or in postmarketing surveillance. For ease and clarity of reference, these conditions will collectively be referred to as "autoimmune conditions" hereafter in this protocol, though it is acknowledged that they are actually a broader group of conditions.
  - Rheumatologic/autoimmune disorders: immune thrombocytopenia (ITP), autoimmune hemolytic anemia (AHA), systemic lupus erythematosus (SLE), rheumatoid arthritis (RA), juvenile rheumatoid arthritis (JRA), psoriatic arthritis, ankylosing spondylitis (AS), reactive arthritis, Crohn's disease, and ulcerative colitis;
  - Autoimmune endocrine conditions: type 1 diabetes, Hashimoto's disease, Graves' disease;
  - Autoimmune neurologic and ophthalmic conditions: multiple sclerosis (MS), acute disseminated encephalomyelitis (ADEM), other demyelinating diseases of the nervous system, Guillain-Barré syndrome (GBS), neuromyelitis optica, optic neuritis, and uveitis.

Protocol/Amendment No.: 070-01

3. To describe the general safety of GARDASILTM on the day of vaccination (i.e., Day 0) among young males by estimating the incidence of the following health outcomes on the day of vaccination, and estimating relative risk of these health outcomes as compared to incidence rates in a post-vaccination self-comparison period:

- Syncope, convulsive syncope;
- Epilepsy, convulsions;
- Head trauma;
- Allergic reactions.

#### 2.3 HYPOTHESES

This is a descriptive observational study designed to provide data on the safety of GARDASILTM in young males in the course of routine clinical practice. No formal hypotheses will be tested.

#### 3. PROTOCOL DETAILS

#### 3.1 STUDY SETTING

This descriptive observational database study will be conducted at patients included in this study will be drawn from a proprietary research database containing eligibility, pharmacy claims, and medical claims data from a large US health plan affiliated with the property of the use of the patient population in the database is geographically diverse across the US and fairly representative of the US population. Underlying information is updated frequently.

Within the PPD database, encounters with the health plan are associated with a combination of provider and procedure codes distinguishing hospitalizations and emergency room visits. For hospitalizations, claims associated with the health outcomes are identified between the beginning and end dates of a hospitalization. Each facility service record contains information on up to nine International Classification of Diseases Ninth Revision (ICD-9) diagnosis codes, with the primary diagnosis listed in the first position, and up to six procedures recorded with ICD-9-CM procedure codes, current procedural terminology (CPT) codes, or Health Care Financing Agency (HCFA) Common Procedure Coding System (HCPCS) codes. The facility transactions contain each service category that the facility (e.g., hospital) listed on its claim for reimbursement, such as surgeries, radiologic procedures, laboratory tests, room and board charges, or other billed items.

The database provides the opportunity to link patient and physician survey data to pharmacy and medical claims, medical record data, socioeconomic measures, and clinical laboratory results.

PPD research activities utilize de-identified data from the research database except in limited instances where applicable law allows the use of patient identifiable data.

The research database affords distinct research advantages. An important advantage is the large number of subjects that can be studied because the data are routinely collected and maintained in computerized data files. The completeness of the data allows investigate and link any number of patient, physician, and treatment attributes, while maintaining the de-identified nature of the data. The database also captures a longitudinal record of medical services, irrespective of treatment site.

Protocol/Amendment No.: 070-01

#### 3.2 INFORMED CONSENT

There will be no active enrollment or active follow-up of the study subjects, and no data will be collected directly from the study subjects. The study protocol will be submitted to an Institutional Review Board (IRB) by PPD for review and approval.

The SPONSOR will not have access to any individual patient's medical information except as part of an audit of the data. Procedures for data audits will be determined. The data will be analyzed by the study investigators and only aggregated data with no personal identifiers will be provided to the SPONSOR.

## 3.3 SAFETY REVIEW COMMITTEE (SRC)

An SRC that is external to the study will consist of independent experts in various relevant areas such as vaccine safety, immunology, pharmacoepidemiology, rheumatology, neurology, pediatric infectious diseases, or adolescent medicine. As much as possible, the SRC will consist of an odd number of voting members to avoid a tie in voting. In case of a tie, where the SRC consists of an even number of members, the SRC chair's vote will prevail. One of the SRC members will be selected as the chairperson in the first SRC meeting and will facilitate the subsequent meetings. The SRC chairperson will be selected by consensus among the SRC members.

The SRC will meet annually (or more often, if deemed necessary) to review data compiled by PPD in preparation for the annual interim reports and the final study report, and to assess any evidence that may be indicative of a potential signal. The assessment of safety will be made based on a process that is pre-specified in the SRC Standard Operating Procedures (SOP). The possible relationship of an event to GARDASILTM will be assessed by the SRC based on statistical and clinical judgment of a range of information elements, including biological plausibility, clinical relevance, statistical strength, adjustment for false discovery rate due to multiple comparisons, temporal relationship, and time distribution of the event after vaccination (i.e., the existence of a cluster or not).

If the SRC determines that the data suggest a potential safety signal, further investigations may be conducted, as requested by the SRC. The investigation can include, but may not be limited to, assessment of the existence of a cluster, additional exploratory data analysis (such as SaTSCAN analysis), or medical record review (for example, to determine if a condition was pre-existing prior to vaccination with GARDASILTM or to determine the nature of the condition resulting in a specific diagnosis code). In addition, the SRC may request case review or adjudication of diagnosis in the general safety portion of the analysis, if it identifies the need for additional information on certain general safety outcomes.

Annual interim study reports will be prepared subsequent to these meetings. The study investigators and the SPONSOR representative(s) will attend the SRC meetings as non-voting, observing members to provide information requested by the SRC and to answer questions that the SRC has about the study. An SOP adapted from that of the

[figure not shown]
GARDASIL female post-licensure safety study will be developed for this study. The SOP will provide details regarding the assembly of the SRC, its roles and responsibilities, and voting procedures. The SOP will incorporate elements of the SPONSOR's Data Safety Monitoring Board Charter, as appropriate. This SOP will be written collaboratively by and the SPONSOR, and approved by the SRC. The SOP will be finalized prior to the first meeting of the SRC, in advance of any review of data analysis undertaken for the study.

#### 3.4 COHORT DEFINITIONS

There will be 2 general safety cohorts and one autoimmune cohort (not mutually exclusive) of males who received GARDASILTM, as described below (Figure 3-1).

Figure 3-1

Males in the Database Vaccinated with GARDASILTM: Study Populations for the Post-licensure Observational Study of the Safety of GARDASILTM in Males

Protocol/Amendment No.: 070-01

19

## 3.4.1 General Safety Cohorts: Regimen Initiators and Regimen Completers

For monitoring general safety, there will be two cohorts:

- 1) **Regimen Initiators:** Males who received at least one GARDASILTM vaccination administered after FDA licensure for males (October 2009). Males in this cohort will be required to be members of the health plan affiliated with "(hereafter referred to as "the health plan") at the time of GARDASILTM receipt.
- 2) Regimen Completers: Male health plan members who received exactly 3 doses of GARDASILTM after FDA licensure for males (October 2009). This cohort will be limited to subjects who received GARDASILTM per protocol (male, 9-26 years of age at time of the first dose, the first and third dose administered within 12 months with intervals of at least 28 days between dose 1 and dose 2, 12 weeks between dose 2 and dose 3, and 24 weeks between dose 1 and dose 3). With the exception of the allowance of a 12-month interval between the first and third doses, this is the administration regimen recommended by the CDC Advisory Committee on Immunization Practices (ACIP) [4]. ACIP specifies a 6-month interval for regimen completion. A 12-month interval was selected for this study to provide sufficient flexibility for accrual within the Regimen Completers cohort, as not all 3-dose completers will adhere exactly to a 6-month completion regimen. Males in this cohort will be required to be continuously enrolled into the health plan (with allowance for standard grace periods that account for brief lapses in membership) through the receipt of all three GARDASILTM doses.

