## SUMMARY OF CHANGES FOR AMENDMENT 1 (CONT.)

Protocol Section	Change				
4.1.2 Relative Risks	Added Table 4-1 to summarize the analyses to be				
	conducted in the study. Added separate analysis of each				
	dose for Regimen Completer cohort, to assist in				
	evaluating dose-specific safety. Removed redundant				
	analyses from Regimen Completer cohort that are already				
	planned for Regimen Initiator cohort (completers are a				
	subset of initiators).				
Global	"Incidence rates" replaced with "incidence" to reflect the				
	possibility that for some analyses with limited person-				
	time, risk ratios (based on number of events per number of				
	subjects) may be used rather than rate ratios.				
Global	Minor editorial revisions for clarification purposes.				

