#### 3.4.3 General Safety and Autoimmune Cohort Exclusion Criteria

As a general rule, all males vaccinated with at least one dose of GARDASILTM after the approval of the male indication in the US will be included in the study.

For the general safety cohorts, the following exclusion criteria will apply:

- any females;
- males vaccinated prior to the FDA date of licensure of GARDASILTM for males for the prevention of external genital warts (October 2009); and/or
- males who received all doses of GARDASILTM outside of the health plan.

Specific to the Regimen Completers cohort, the following additional exclusion criteria will also apply:

- any male outside the 9-26 year old age range at first dose;
- males who were not health plan members at each GARDASILTM dose;
- males who completed the 3-dose regimen of GARDASILTM over a period greater than 12 months;
- males who had less than a 28-day interval between the first and second dose;
- males who had less than 12 weeks between the second and third dose; and/or
- males who had less than 24 weeks between the first and third dose.

For the autoimmune cohort of males vaccinated with GARDASILTM, the following exclusion criteria will apply (i.e., same as for general safety plus requirement of 12 months of health plan membership prior to vaccination):

- any females;
- males vaccinated prior to the FDA date of licensure of GARDASILTM for males for the prevention of external genital warts (October 2009);
- males who received all doses of GARDASILTM outside of the health plan; and/or
- males with less than 12 months of health plan membership prior to their first dose of GARDASILTM.

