#### 4.1 DATA ANALYSIS FOR GENERAL SAFETY COHORTS

#### 4.1.1 Incidence

The incidence of all health outcomes that result in a hospitalization or emergency room visit during the risk and self-comparison periods will be described. Incidence will be calculated separately for health outcomes associated with hospitalizations and emergency room visits, as well as for hospitalizations and emergency room visits combined. For the analysis using combined hospitalizations and emergency room visits, if an emergency room visit results in a hospitalization for the same health care event, the event will be counted once to avoid duplication.

For each subject, the incidence of a health outcome in a given risk or self-comparison period will be defined as the first occurrence in the database of a code of the health outcome HCUP category, if any, during this study period. For each health outcome category, the incidence in both the risk and the post-vaccination self-comparison periods will be calculated as the number of first occurrences of the health outcome divided by the total person-time accrued from the study subjects under observation. For each event, accrued person-time for an individual will be calculated as the total number of days from the beginning of the risk or self-comparison period and ending at the earliest of: the end of the period, receipt of a subsequent dose of GARDASILTM, termination of membership in the health plan, occurrence of the health outcome of interest, death, or, for interim annual reports only, attainment of the pre-specified cut-off date for the report. A subject can have partially-missing risk or self-comparison periods and still be part of the analysis.

For analyses in which subjects may have more than one dose, each subject can contribute only once for each specific health outcome throughout the combined risk periods (i.e., maximum of one occurrence of each health outcome taken into account for each study subject). The denominator will be the combined at risk person-time accrued throughout the number of risk periods (or corresponding self-comparison periods) available for a given individual (censored upon occurrence of the outcome), which will depend on the number of doses received.

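### The only dose-2-specific estimate is made in Regimen Completers, so it is conditional on what happens after the dose-2 risk window

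*Protocol*

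**What the plan says.** Section 3.4.1 of the protocol defines two general safety cohorts. Initiators are "Males who received at least one GARDASIL" vaccination after licensure for males, with membership at the time of receipt. Completers are "Regimen Completers: Male health plan members who received exactly 3 doses of" the vaccine, at minimum intervals, with enrolment required "through the receipt of all three GARDASIL" doses. Section 3.4.3 repeats the timing limit by excluding males who finished the regimen "over a period greater than 12 months".

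Table 4-1 assigns a cohort to each self-comparison analysis:

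- Initiators: all doses combined, and dose 1.
- Completers: doses 1, 2 and 3, each separately, for Days 1-60 and Days 1-14.

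The Completer dose-by-dose analysis came in with Amendment 1 ("Added separate analysis of each" dose), and the stated purpose was to help evaluate safety by dose.

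The objectives rest on the Initiator rows. The primary objective (Section 2.1) concerns outcomes "occurring in combined 60-day risk periods after each dose of GARDASIL"; secondary objective 1 (Section 2.2) concerns outcomes "in the 60-day risk period following the first dose of GARDASIL". Under Section 4.1.1, an Initiator's person-time in a multi-dose analysis is the time from the doses he actually had, "which will depend on the number of doses received".

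**The concern.** Whether a male counts as a Completer is not known when he receives dose 2. It is settled later, by whether he receives dose 3 in time and stays enrolled. An event after dose 2 can itself change that: he may stop the series, have dose 3 too late, or leave the plan. Such a male is then dropped from the dose-2 analysis because of the outcome that the analysis is meant to count.

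For dose 1 there is an unselected counterpart, the Initiator Dose 1 row. For dose 2 there is none. At stake is whether the one dose-2 estimate given to the Safety Review Committee can be read as the experience of all males who received a second dose. As planned it cannot, and nothing in Table 4-1 warns of this.

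Section 3.7.1 argues that self-comparison spreads characteristics evenly between exposed and unexposed time. That deals with confounding by fixed characteristics. It does not deal with selection on a later consequence of the event.

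**Working it through.** The plan gives no figure for this selection, so there is none to reproduce. The check sets the time windows side by side and then works through an illustration.

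**Step 1. Does the dose-2 risk window precede the selection?** Completers need at least 12 weeks between doses 2 and 3 (Section 3.4.1), which is 12 × 7 = 84 days. The risk window is 60 days. It therefore always closes before dose 3, and every dose-2 risk-window event in this row comes from a male who went on to complete.

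**Step 2. Where does the comparison time fall?** It starts 91 days after each dose (Section 3.7.1). In the example under Figure 3-2 it covers months 5 to 6 and 9 to 14, that is 1 + 5 = 6 months, in line with the 180 days mentioned in Section 3.7.1. One month precedes dose 3 and five follow it. Events in those five months cannot affect receipt of dose 3.

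**Step 3. Size with pooled comparison time.** Let s = P(completes | event in the window) / P(completes | no such event). The protocol gives no value for s, so the values below are assumptions.

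- If no comparison time is filtered: observed RR = true RR × s.
- If the filter also acts on the 1/6 of comparison time before dose 3: observed RR = true RR × s / (s/6 + 5/6).

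For a true RR of 2:

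| s | first formula | second formula |
|---|---|---|
| 0.9 | 2 × 0.9 = 1.80 | 1.80 / 0.983 = 1.83 |
| 0.75 | 2 × 0.75 = 1.50 | 1.50 / 0.958 = 1.57 |
| 0.5 | 2 × 0.5 = 1.00 | 1.00 / 0.917 = 1.09 |

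**Step 4. Comparison time between doses 2 and 3 only.** Observed RR = true RR × (s for risk-window events) / (s for comparison-window events). If the two are equal they cancel. If events nearer to dose 3 deter more, the ratio exceeds 1 and the bias reverses. Under this option a Completer at the minimum interval has no such comparison time, since 84 days is less than 91.

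**Step 5. What the Initiator combined analysis recovers.** It keeps the events but mixes them with the other doses. Assume 135,000 first doses and 44,000 third doses (the two accrual caps in Section 3.5, taken together for illustration), between 44,000 and 135,000 second doses, equal background rates and windows, and RR 2 after dose 2 only. Pooled RR = (179,000 + 2·n2) / (179,000 + n2):

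- n2 = 44,000: 267,000 / 223,000 = 1.20.
- n2 = 135,000: 449,000 / 314,000 = 1.43.

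**The case against.** The strongest reply is that little is actually lost. Initiators need only one dose, so males who stopped after dose 1 are in the Initiator Dose 1 row, and males who stopped after dose 2 are in the combined analysis. No stated objective asks for a dose-2-only estimate. Deaths are tabulated for every study subject regardless of completion (Section 4.1.4), and the Safety Review Committee may ask for further analyses (Section 3.3). All of this stands. It confines the point to the dose-2 estimate, and to the labelling of the Completer dose-1 row.

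The second reply is that the direction of the bias is not fixed. Section 4.1.1 speaks of corresponding self-comparison periods and ends person-time at the next dose, while Section 3.7.1 leaves details to the Data Analysis Plan. If the dose-2 row uses only the window before dose 3, the filter acts on both sides (Step 4). This also stands, so bias toward no harm can be stated only for pooled comparison time.

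Three stronger readings are tempting and not supported:

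- A reader might infer that events after dose 1 that led to stopping are removed from the study. Only the Completer dose-1 row drops them.
- A reader might infer that the dose-3 estimate is biased in the same way. No later dose is required, so this mechanism removes no dose-3 events.
- A reader might take low power as support. With 44,000 doses and a background of 1 per 12,000, a mid-P test has 17.5% power for RR 2 and 48.0% for RR 3 with equal comparison time, or 28% and 68% with three times as much. Those figures concern precision and say nothing about selection.

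**Conclusion.** The point holds for dose 2. Table 4-1 and Sections 3.4.1 and 3.4.3 together make the study's only dose-2-specific estimate conditional on later completion. This is fixed in the protocol's own assignment of cohorts to analyses, so it is not a detail left open for the Data Analysis Plan. The primary objective and secondary objective 1 are unaffected.

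With pooled comparison time the bias is toward no harm, and a true RR of 2 would appear as about 1.8, 1.5–1.6 or 1.0–1.1 for s of 0.9, 0.75 or 0.5. Those values of s are illustrative, and the second figure in each range also relies on the 1:5 split of comparison time in the Figure 3-2 example. With comparison time restricted to the interval between doses 2 and 3, neither direction nor size can be stated. The change is worth making because it is cheap and no other row gives an unselected dose-2 result; it does not call the main analyses into question.

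**What to change.** In Table 4-1, add a Regimen Initiator self-comparison row for dose 2, covering all Initiators who received a second dose, for Days 1-60 and Days 1-14. Make it the main dose-2 result. Keep the Completer rows, and label those for dose 1 and dose 2 as conditional on completing the regimen.

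The cost is one more row, from males and doses already in the Initiator cohort. The small downside is that second doses given off the recommended interval enter the estimate; the Completer row still shows the on-schedule subset. An Initiator row for dose 3 is optional and is not needed to remove this bias.
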